### **7.1.4 Patient Monitoring During and After Tafasitamab Infusion**

Vital signs should be measured as outlined in [Section 9.4.1](#).

All supportive measures consistent with optimal patient care will be provided throughout the study according to institution standards. The observation of patients after the infusion is recommended, however, the duration and potential monitoring of vital signs should be determined by the investigator based on clinical judgement in accordance with local/practice guidelines of the institution. The Sponsor recommends that the investigators consider hospitalization on C1D15 for patients who experienced infusion related events during previous infusions on C1D1, C1D4 and/or C1D8 with 12 mg/kg tafasitamab or if otherwise clinically indicated.

Precautions for anaphylaxis should be observed during tafasitamab administration. Emergency resuscitation equipment and medications should be readily available.

Additional supportive measures should also be available and may include, but are not limited to, epinephrine, antihistamines, corticosteroids, i.v. fluids, vasopressors, oxygen, bronchodilators, diphenhydramine, and acetaminophen (paracetamol).

In case of hospitalization of patient as a prophylactic measure in accordance with local/practice guidelines of the institution will not be reported as AE/SAE.

## **7.2 Standard of Care**

Not applicable.

## **7.3 Dose Modifications, Drug Interruptions and Discontinuation**

### **7.3.1 Tafasitamab Specific Dose Modifications, Drug Interruptions and Discontinuation**

Intra-patient dose reductions of tafasitamab are not permitted. Drug interruptions or discontinuation may occur e.g. in case of severe IRRs, Cytokine Release Syndrome (CRS), allergic reactions, infections, febrile neutropenia or severe hematologic toxicity. If a tafasitamab infusion is delayed due to toxicity for more than 2 days during treatment Cycle 1 or for more than 7 days during treatment Cycles 2 and 3, this infusion should be skipped and tafasitamab treatment continued only at the next scheduled timepoint. In case 2 consecutive tafasitamab doses are skipped during the first three treatment Cycles, study drugs will be discontinued, and the EOT visit will be performed. See [Table 14](#) and [Table 15](#) for additional details.

For further details on the management of tafasitamab IRRs and CRS, please see [Table 12](#).

#### **7.3.1.1 Management of Tafasitamab IRRs and Cytokine Release Syndrome (CRS)**

IRRs and CRS will be defined according to the NCI-CTCAE, version 5.0 definition of IRR and CRS (see [Table 12](#)).

**Table 12: Definition of IRR and CRS NCI-CTCAE Version 5.0: IRR and CRS**

AE	Grade 1	Grade 2	Grade 3	Grade 4
IRR	Mild transient reaction; infusion interruption not indicated; intervention not indicated	Therapy or infusion interruption indicated but responds promptly to symptomatic treatment (e.g., antihistamines, NSAIDs, narcotics, i.v. fluids); prophylactic medications indicated for ≤ 24 hours	Prolonged (i.e. not rapidly responsive to symptomatic medication, brief interruption of infusion, or both); recurrence of symptoms following initial improvement; hospitalization indicated for clinical sequelae	Life-threatening consequences; urgent intervention indicated
CRS	Fever with or without constitutional symptoms	Hypotension responding to fluids; hypoxia responding to < 40% O 2 	Hypotension managed with one pressor; hypoxia requiring ≥ 40% O 2 	Life-threatening consequences; urgent intervention indicated

Abbreviations: CRS=cytokine release syndrome; IRR=infusion-related reaction; i.v.=intravenous; NCI-CTCAE= National Cancer Institute Common Terminology Criteria for Adverse Events; NSAIDs=non-steroidal anti-inflammatories.

**Please note:** An acute infusion reaction may occur with an agent that causes cytokine release (e.g., monoclonal antibodies or other biological agents). Signs and symptoms usually develop during or shortly after drug infusion and generally resolve completely within 24 hours of completion of infusion. Signs/symptoms may include: allergic reaction/hypersensitivity (including drug fever), arthralgia (joint pain), bronchospasm, cough, dizziness, dyspnoea, fatigue (asthenia, lethargy, malaise), headache, hypertension, hypotension, myalgia, nausea, pruritus/itching, rash/desquamation, rigors/chills, sweating (diaphoresis), tachycardia, tumor pain (onset or exacerbation of tumor pain due to treatment), urticaria (hives, welts, wheals), and vomiting.

Applied e.g. via breathing mask.

**7.3.1.2 Interventions for Grade 2 IRRs, Grade 1 CRSs**

If a patient presents with a grade 2 infusion reaction or grade 1 CRS:

- The infusion should be stopped immediately
- The patient should receive appropriate treatment with an antihistamine and/or acetaminophen (paracetamol) or methylprednisolone (or equivalent) as clinically indicated
- Once the symptoms have been resolved or IRR reduced from Grade 2 to Grade 1, according to investigator assessment, the infusion can be continued at an infusion rate of 50% of the speed so far. If, after one hour, the patient's symptoms do not return and vital signs are stable, the infusion rate may be increased every 30 minutes, as tolerated, to the baseline rate
- If a patient receives further infusions of tafasitamab, then pre-medication should be given before all subsequent infusions of tafasitamab throughout the study

**7.3.1.3 Interventions for Grade 3 IRRs, Grade 2 CRSs**

If a patient presents with a grade 3 IRR or grade 2 CRS:

- The infusion should be stopped immediately
- The patient must receive appropriate treatment with an antihistamine and/or acetaminophen (paracetamol) or methylprednisolone (or equivalent) and, if necessary, further medications (i.e. epinephrine, bronchodilator) as clinically indicated
- Only after the complete resolution of all symptoms, and after having received appropriate prophylactic medication(s), the infusion may be resumed at an infusion rate of 25% of the speed so far. If, after 1 hour, the patient's symptoms do not return and vital signs are stable, the infusion rate may be increased to a maximum of 50% of the baseline speed
- If, after the resumption of the infusion, symptoms return (irrespective of grade), the infusion must be stopped immediately and the infusion tubing should be disconnected from the patient
- Based on the investigator's decision the patient may receive further infusions of tafasitamab provided clinically appropriate precautions are undertaken. Pre-medication should be given before all subsequent infusions of tafasitamab throughout the study

If precluded from further tafasitamab administrations, the patient may continue treatment with lenalidomide.

**7.3.1.4 Interventions for Grade 4 IRRs, Grade 3 CRSs, Grade 4 CRSs**

If a patient presents with a grade 4 infusion reaction or grade 3-4 CRS:

- The infusion should be stopped immediately, and the infusion tubing should be disconnected from the patient
- The patient must receive appropriate treatment with an antihistamine and/or acetaminophen (paracetamol) or methylprednisolone (or equivalent) and, if necessary, further medications (i.e. epinephrine, bronchodilator) as clinically indicated
- The patient must not receive any further tafasitamab infusions but may continue treatment with LEN

**7.3.2 LEN Specific Dose Modifications, Drug Interruptions and Discontinuation**

LEN may be given only on Days 1 to 21 of each cycle up to 12 cycles in total and must not be administered beyond this period.

In case of LEN-related toxicity (e.g., neutropenia), the dose of LEN may be interrupted temporarily and/or reduced successively level by level from the starting dose of 25 mg daily as described below in [Table 13](#).

**Table 13: LEN Dose Modification Guidelines**

Starting Dose	25 mg Daily on Days 1–21, Every 28 Days
Dose Level – 1	20 mg daily on Days 1–21, every 28 days
Dose Level – 2	15 mg daily on Days 1–21, every 28 days
Dose Level – 3	10 mg daily on Days 1–21, every 28 days
Dose Level – 4	5 mg daily on Days 1–21, every 28 days

Patients who cannot tolerate Dose Level – 4 are to be discontinued from LEN treatment in the study but should continue therapy with tafasitamab alone.

If LEN dosing was interrupted during the previous cycle and was restarted with a one-level dose reduction without requiring an interruption for the remainder of the cycle, then that reduced dose level will be initiated on Day 1 of the new cycle. There will be no more than one dose reduction from one cycle to the next. Once a patient's LEN dose has been reduced, no dose re-escalation is permitted.

### **7.3.3 General Dose Modifications, Drug Interruptions and Discontinuation due to Toxicity**

The next cycle of treatment may begin on the scheduled Day 1 if all of the following criteria are met:

- ANC is  $\geq 1,000/\text{mm}^3$  (unless neutropenia is due to infiltration of bone marrow)
- Platelets (PLT)  $\geq 50,000/\text{mm}^3$  (unless thrombocytopenia is due to infiltration of bone marrow, patient may have received transfusion) and absence of active bleeding
- No other treatment related toxicities  $>$  Grade 2

If, based on medical judgment, the treating physician considers a change in laboratory parameter or AE not to be a study drug-related toxicity, but to represent a natural fluctuation in or progression of the underlying disease, then it is at the physician's discretion and assessment of the individual risk/benefit ratio to determine whether the patient should be dosed. The decision and rationale behind the decision should be documented in the source data.

If any of the above conditions are not met on Day 1 of a new cycle, the patient will be monitored as per institutional guidelines and a new cycle will be initiated when all criteria listed above are met. Specific course of action for a given toxicity occurring in the course of the treatment cycle is described below.

If initiation of the next planned Cycle is delayed by  $>$  28 days for the same persistent study drug-related toxicity, then study drugs will be discontinued, and the EOT visit will be performed.

#### ***7.3.3.1 Hematological and Other Toxicities***

Patients will be evaluated for AEs at each visit with the NCI CTCAE v5.0 used as a guide for grading severity. The dose and/or administration of study drug(s) for each patient will be interrupted and/or modified following toxicity as described below in [Table 14](#) and [Table 15](#) and [Table 13](#) for LEN dose reduction instructions.

**Table 14: Hematological Toxicities**

Hematological Toxicity	LEN 	Tafasitamab
Neutropenia Grade 4 (ANC < 500/μl) with or without a temperature of ≥ 38.0°C/100.4°F	Interrupt LEN.	Withhold tafasitamab infusion.
	If neutropenia has resolved to ≤ Grade 2 (ANC ≥ 1,000/μl) within 7 days, LEN should be restarted in the next cycle at the same dose. If neutropenia has not resolved to ≤ Grade 2 within 7 days, LEN should be resumed in the next cycle at the next lower dose level (see Table 13 above). Monitor CBC at least QW until neutrophil count is ≥ 1,000/μl.	If neutropenia has resolved to ≤ Grade 2, resume tafasitamab. Monitor CBC at least QW until neutrophil count is ≥ 1,000/μl.
Neutropenia Grade 3 (ANC < 1,000/μl) > 7 days	LEN should be resumed in the next cycle at the next lower dose level (see Table 13 above).	Hold tafasitamab until resolved to ≤ Grade 2 (ANC ≥ 1,000/μl).
Neutropenia Grade 3 (ANC < 1,000/μl) with a temperature of ≥ 38.0°C/100.4°F (Febrile Neutropenia)	Interrupt LEN.	Interrupt tafasitamab.
	If infection is resolving (< 38°C/100.4°F), and neutropenia has resolved to ≤ Grade 2, LEN should be resumed in next cycle at the next lower dose level (see Table 13 above).	If infection is resolving (< 38°C/100.4°F), continue tafasitamab as per protocol.
Neutropenia < Grade 3 associated with infection ≥ Grade 3 or fever (≥ 38.0°C body temperature)	First occurrence interrupt LEN.	Interrupt tafasitamab.
	If infection is resolving (< 38°C/100.4°F), LEN should be restarted in the next cycle at the same dose.	If infection is resolving (< 38°C/100.4°F), continue tafasitamab per protocol.
	Re-occurrence: interrupt LEN. If infection is resolving (< 38°C/100.4°F), LEN should be restarted in the next cycle at the next lower dose level.	
Thrombocytopenia Grade 3-4 (PLT < 50,000/μl) with or without bleeding	Interrupt VTE prophylaxis.	
	Consider platelet transfusion according to institutional guidelines. If thrombocytopenia has resolved to ≤ grade 1, consider change of VTE prophylaxis agent (e.g. change antiplatelet agent to low molecular weight heparin). VTE prophylaxis should be tailored to the patient's individual risk/benefit profile by taking into account the individual thrombotic risk and bleeding risk.	
	Interrupt LEN Follow CBC at least every 7 days. If thrombocytopenia has resolved to ≤ Grade 2 (PLT ≥ 50,000/μl), LEN should be resumed in the next cycle at the next lower dose level (see Table 13 for LEN dosing).	Withhold tafasitamab infusion Follow CBC at least every 7 days. If thrombocytopenia has resolved to ≤ Grade 2 (PLT ≥ 50,000/μl), restart tafasitamab. Monitor as clinically indicated.
Anemia Grade 3-4 (Hemoglobin <8.0 g/dL)	Interrupt LEN Consider transfusion according to institutional guidelines Urgent intervention indicated as per local institutional guidance	Interrupt Tafasitamab Consider transfusion according to institutional guidelines Urgent intervention indicated as per local institutional guidance

Abbreviations: AE=adverse event; ANC=absolute neutrophil count; CBC=complete blood count; VTE=venous thromboembolism; LEN=lenalidomide; PLT=platelets. QW=weekly

If, based on medical judgment, the treating physician considers a laboratory parameter change or AE not to be a study drug-related toxicity, but to represent a natural fluctuation in or progression of the underlying disease, then it is at the physician's discretion and assessment of the individual risk/benefit ratio to determine whether the patient should be dosed. The decision and rationale behind the decision should be documented in the source data.

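### Table 14 both holds and continues tafasitamab at a mid-cycle infusion when Grade 3 febrile neutropenia has outlasted 7 days and the fever has gone, and no rule says which row governs

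*Protocol*

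**What the plan says.** Protocol Section 7.3.3.1 sends sites to Table 14 for dose changes after haematological toxicity and uses CTCAE v5.0 as the guide to grading. Three of its neutropenia rows matter here.

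- Grade 4 row. The trigger is "Neutropenia Grade 4 (ANC < 500/μl) with or without a temperature of ≥ 38.0°C/100.4°F". For LEN, on recovery to Grade 2 or better "within 7 days, LEN should be restarted in the next cycle at the same dose"; otherwise, "If neutropenia has not resolved to ≤ Grade 2 within 7 days, LEN should be resumed in the next cycle at the next lower" level. For tafasitamab: "If neutropenia has resolved to ≤ Grade 2, resume tafasitamab".
- Grade 3 beyond 7 days. LEN resumes one level lower. For tafasitamab: "Hold tafasitamab until resolved to ≤ Grade 2", that is, until ANC is at least 1,000/μl. Fever is not mentioned.
- Grade 3 febrile. The trigger is "Neutropenia Grade 3 (ANC < 1,000/μl) with a temperature of ≥ 38.0°C/100.4°F (Febrile Neutropenia"). Once the fever is settling and ANC has recovered, "LEN should be resumed in next cycle at the next lower dose level". For tafasitamab, interrupt, then: "If infection is resolving (< 38°C/100.4°F), continue tafasitamab as per protocol". Duration is not mentioned.

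Section 7.3.3 requires ANC of at least 1,000/mm³ to begin a new cycle. Section 7.3.1 says when a delayed tafasitamab infusion is skipped, and ends study drugs after two consecutive skips in the first three cycles.

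**The concern.** The two Grade 3 rows overlap: one is defined by duration, the other by fever, and an episode can have both. Section 5.2 lists Grade 3 or higher neutropenia with fever lasting more than 7 days among the pre-defined safety events, so the protocol itself foresees the combination.

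Where the rows overlap, two sites can follow the table faithfully and do opposite things with the next infusion. The SAP tabulates skipped tafasitamab doses and LEN reductions (Sections 6.4.4.1 and 6.4.4.4) and the TEAEs leading to skips, reductions and discontinuations (Section 10.2.4.1.2). In a small trial whose primary objective is safety and tolerability, those summaries would partly record which row a site read.

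**Working it through.** There is no planned figure to reproduce. The check sets the rows side by side and goes through the possible patient states.

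| Row | Trigger | LEN | Tafasitamab |
|---|---|---|---|
| Grade 4 | ANC < 500/μl, fever or not | same dose if recovered within 7 days, otherwise one level lower | withhold until ANC recovers |
| Grade 3, > 7 days | ANC < 1,000/μl for > 7 days | one level lower | withhold until ANC ≥ 1,000/μl |
| Grade 3 febrile | ANC < 1,000/μl and ≥ 38.0°C | one level lower | withhold until < 38°C |

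**Tafasitamab.** Take Grade 3 neutropenia (for example nadir 800/μl) that was febrile and has lasted more than 7 days. Both Grade 3 rows apply.

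1. Still febrile, ANC < 1,000: both rows withhold.
2. Below 38°C, ANC ≥ 1,000: both rows allow the infusion.
3. Below 38°C, ANC < 1,000: the duration row withholds and the febrile row continues. This is a direct conflict.
4. Still febrile, ANC ≥ 1,000: the duration row lifts its hold and the febrile row does not. I put no weight on this state, because Table 14 also interrupts tafasitamab for milder neutropenia with fever.

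**Does anything settle state 3?** Table 14 states no row order. The ANC criterion in Section 7.3.3 governs only the start of a cycle. Footnote 1 gives discretion only for changes judged not drug-related. So a drug-related event at a mid-cycle infusion is left open. On the visible schedule (Schedule of Assessments; SAP Section 6.4.2.4.3) infusions after Day 1 fall in Cycles 1 to 3.

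**What can follow.** Section 7.3.1 skips an infusion delayed for toxicity by more than 2 days in Cycle 1 or more than 7 days in Cycles 2 and 3. Suppose Grade 3 febrile neutropenia begins on Cycle 1 Day 5 and the Day 8 infusion is skipped. On Day 15, 10 days after onset, the patient is afebrile with ANC 700/μl. The febrile row gives the infusion. The duration row holds it, and if recovery takes more than 2 further days this is the second consecutive skip and study drugs are discontinued.

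**LEN.** Compare two febrile patients who both recover within 7 days. With nadir 400/μl the Grade 4 row restarts at the same dose; with nadir 800/μl the Grade 3 febrile row restarts one level lower. Beyond 7 days both go one level lower, so the inversion is confined to quick recovery. With one grade per nadir, no patient receives two LEN orders. If the cut-off of 1,000/μl in the febrile row is read without a lower bound, the patient at 400/μl meets both rows and does receive two.

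**Size.** Inputs: 5 of 81 patients with tafasitamab-related febrile neutropenia in L-MIND (Protocol Table 7), and about 51 patients planned.

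- Expected febrile neutropenia: 5/81 × 51 = 3.1, about 3 patients.
- Largest LEN difference for one patient: a Cycle 1 event, then one level (25 − 20 = 5 mg) on 21 days of 11 cycles, with no re-escalation (Section 7.3.2): 5 × 21 × 11 = 1,155 mg of 25 × 21 × 11 = 5,775 mg, or 20%.

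**The case against.** The strongest reply on tafasitamab is that the febrile row merely lifts the interruption made for fever: continuing as the protocol directs would leave the duration row's ANC hold in force. That is a reasonable reading, but the text does not require it. In the same febrile row the LEN cell names ANC recovery as a condition and the tafasitamab cell does not, so a site may take the omission as intended. The reply also notes how narrow the overlap is: Grade 3, febrile, beyond 7 days, fever gone, ANC not recovered, and a mid-cycle infusion due. That stands and limits the size.

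On LEN, a reader might infer that a febrile Grade 4 patient is given two different doses. The documents do not support that as the natural reading. The Grade 4 row expressly covers febrile cases, the other row is labelled Grade 3, and a nadir of 400/μl is Grade 4 by the table's own definition. What remains is an ordering that looks inverted, plus a cut-off printed without a lower bound. Whether the ordering is clinically appropriate is not a question for this review.

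A reader might also infer that the primary endpoint is compromised. The index event precedes the dosing decision, the primary estimand counts TEAEs regardless of dose modification, and SAP Section 10.2.4.1.1 counts a participant once per TEAE at the worst grade. A recurrence could change worst grade or event counts, but a repeat of the same TEAE does not raise participant incidence. The clearer exposure is in the dosing and discontinuation summaries.

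**Conclusion.** The tafasitamab conflict is real in the current text and does not depend on how the grade bands are read. It applies to a drug-related Grade 3 febrile episode beyond 7 days, at a within-cycle infusion, once temperature is below 38°C with ANC under 1,000/μl. The LEN point is secondary: an ordering inversion for febrile episodes recovering within 7 days, and a direct conflict only on the unbounded reading of the Grade 3 cut-off.

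Few patients are involved. About 3 of 51 is a guide to febrile neutropenia of any kind, and the number in conflict is an unknown part of it. It assumes that the L-MIND rate, for tafasitamab-related events at 12 mg/kg, carries over to this regimen. A reader might instead scale the L-MIND neutropenia count (30/81 × 51 = 18.9, about 19 patients), but that includes afebrile neutropenia, and both points here require fever. The 1,155 mg (20%) is a single-patient maximum: a Cycle 1 event, LEN through Cycle 12 and no other modification. It is not an expected effect.

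The point still merits correction despite the small numbers. These are binding dosing instructions for a foreseeable serious toxicity, and the row chosen can lead to discontinuation of study drugs.

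**What to change.** The sponsor should reconcile the Table 14 neutropenia rows so that each combination of grade, fever and duration leads to one instruction per drug, or add a line saying which row governs when two apply. Specifically:

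- state which tafasitamab instruction applies when Grade 3 neutropenia has been febrile and has lasted more than 7 days, and whether the febrile row carries an ANC condition;
- confirm whether the LEN ordering between the Grade 4 and Grade 3 febrile rows is intended for episodes recovering within 7 days;
- state whether the Grade 3 rows exclude ANC below 500/μl.

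The choice of rule is the sponsor's. The cost is table wording in the next amendment and a clarification letter to sites; no procedure or patient is added.

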**Table 15: Non-Hematological Toxicities**

Non-hematological toxicity	LEN 	Tafasitamab
Thromboembolic events ≥ Grade 3	Discontinue LEN permanently.	Continue tafasitamab infusion as per protocol if clinically appropriate.
Allergic reaction or hypersensitivity Grade 2	If related to LEN then interrupt/skip the dose.	If related to tafasitamab then interrupt/skip the dose.
	Note: if the causality cannot be determined, and the AE may be related to LEN and/or tafasitamab, both drugs should be held.	
	If toxicity resolves to ≤ Grade 1, restart LEN at the next lower dose level (see Table 13 above).	If toxicity resolves to ≤ Grade 1, tafasitamab may be resumed.
Allergic reaction or hypersensitivity ≥ Grade 3	If related to LEN then discontinue permanently.	If related to tafasitamab then discontinue permanently.
	Note: If the causality cannot be determined and the AE may be related to LEN and/or tafasitamab, discontinue both drugs permanently.	
Rash Grade 2 or 3 non-desquamating (blistering)	If related to LEN then interrupt the dose.	If related to tafasitamab then interrupt the dose.
	If the AE resolves to ≤ Grade 1, restart LEN at the same level (see Table 13 above).	If toxicity resolves to ≤ Grade 1, tafasitamab may be resumed.
	Note: if the causality cannot be determined, and the AE may be related to LEN and/or tafasitamab, interrupt both drugs.	
Rash Desquamating (blistering) ≥ Grade 3 OR Non-desquamating Grade 4	If related to LEN then discontinue permanently.	If related to tafasitamab then discontinue permanently.
	Note: If the causality cannot be determined and the AE may be related to LEN and/or tafasitamab, discontinue both drugs permanently.	
TFR Grade 3–4 	Interrupt LEN. If the AE resolves to grade ≤ 1, restart LEN and maintain the same dose level (see Table 13 above).	Continue tafasitamab infusion as per protocol if clinically appropriate.
TFR Grade 1–2 	Continue LEN.	Continue tafasitamab infusion as per protocol.
Constipation ≥ Grade 3	Interrupt LEN. If the AE resolves to ≤ Grade 2, restart at same dose level.	Continue tafasitamab infusion as per protocol if clinically appropriate.
Other non-hematologic AEs ≥ Grade 3	Interrupt LEN. If the AE resolves to ≤ Grade 2, restart at the same or next lower dose level per the investigator's discretion.	Continue tafasitamab infusion as per protocol if clinically appropriate.
Other LEN related AEs in patients with moderate renal impairment (creatinine CL 59-30 mL/min)	If the AE resolves to ≤ grade 2, restart at the same or next lower dose level per the investigator's discretion (see Table 13 above).	Continue tafasitamab infusion as per protocol if clinically appropriate.
Creatinine CL decreases to < 30 mL/min	Interrupt LEN during the current cycle. If creatinine CL ≥ 30 mL/min in the next cycle, restart at the next lower dose level.	Continue tafasitamab/ infusion as per protocol if clinically appropriate.

Abbreviations: AE(s)=adverse event(s); LEN=lenalidomide; NCI-CTCAE=National Cancer Institute Common Terminology Criteria for Adverse Events; TFR=tumor flare reaction.

If, based on medical judgment, the treating physician considers a laboratory parameter change or AE not to be a study drug-related toxicity, but to represent a natural fluctuation in or progression/relapse of the underlying disease, then it is at the physician's discretion and assessment of the individual risk/benefit ratio to determine whether the patient should be dosed. The decision and rationale behind the decision should be documented in the source data.

Tumor flare reaction is defined as constellation of signs and symptoms in direct relation to initiation of therapy. The symptoms/signs include tumor pain, inflammation of visible tumor, hypercalcemia, diffuse bone pain, and electrolyte disturbances (TFR is the only AE that will be graded using NCI-CTCAE version 3.0).

Grade 1: Mild pain not interfering with function; Grade 2: Moderate pain; pain or analgesics interfering with function but not with activities of daily living.; Grade 3: Severe pain; pain or analgesics interfering with function and interfering with activities of daily living; Grade 4: Disabling.; Grade 5: Death.

